### **Clinical studies**

A first-in-man, Phase I single ascending dose (SAD) and multiple ascending dose (MAD) study (ANB020-001) in healthy subjects is being performed. The SAD part of the study has been completed and 64 subjects were enrolled in the SAD part. Dosed cohorts in the SAD part included 10, 40, 100, and 300 mg SC and 40, 100, 300, and 750 mg IV (n=32 SC route, n=32 IV route). No significant changes in the vital signs (blood pressure [BP], heart rate [HR], or body temperature), physical examinations, or electrocardiograms (ECG) were noted. A total of 81%

subjects in the placebo group and 79% subjects in the ANB020 group had at least one treatment-emergent adverse event (TEAE) during the study. The most commonly reported TEAEs were upper respiratory infection (50% versus 48% in placebo and ANB020 group, respectively) and headache (31% versus 27% in placebo and ANB020 group, respectively). One serious adverse event (SAE) of decreased neutrophils was reported in the ANB020 750 mg dose group which resolved without sequelae prior to study completion. This event was also considered a serious unexpected adverse reaction and was deemed possibly related to the study treatment. No other observations of decreased neutrophils lower than  $1.5 \times 10^9/L$  were observed. One subject in the ANB020 40 mg dose group, had an increased troponin level which returned to normal prior to study completion. No other significant changes in the laboratory test results were noted.

The PK and pharmacodynamic (PD) data obtained from the Phase I study (ANB020-001, SAD part) have been utilized to determine the route and dose of ANB020 to be used in this study. The PK data generated indicated that a linear PK profile was observed upon ANB020 administration across the dose ranges investigated, regardless of the route, but with less than dose-proportional increases in exposure for the SC dosing. The estimated ANB020 mean terminal  $t_{1/2}$  ranged approximately 14 to 17 days. Persistent and nearly complete inhibition of ex vivo IL-33 stimulated INF- $\gamma$  production in whole blood was observed following a single dose (except 10 mg SC) as soon as 24 hours, and lasting through 84 days (latest time point observed for 300 mg and 750 mg IV).

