As ANB020 is a mAb, based on clinical studies with other mAbs, study participants may experience symptoms of an apparent allergic reaction to the drug, also known as ‘cytokine release syndrome’. The symptoms of this vary dramatically but can include:

- Mild to moderate fever, chills, headache, nausea, and vomiting.
- Moderate to severe symptoms such as edema, hypotension, and pulmonary infiltrates (e.g. blood and mucus in the lung).

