## 5.0 STUDY TREATMENTS

### 5.1 Treatments Administered

ANB020 is a humanized IgG1/kappa mAb and was selected from a panel of mouse mAb humanized by complementarity-determining region-grafting, optimized and matured via mammalian cell display and somatic hyper mutation using AnaptysBio's (SHM)-XEL™ system to achieve a desired functional inhibitory potency.

ANB020 will be administered to patients by IV infusion in polyvinyl chloride or polyolefin bags following dilution to a total volume of 100 mL with sterile normal saline (0.9% sodium chloride [NaCl]). Placebo will be administered by IV infusion as 100 mL sterile normal saline (0.9% NaCl). Infusions will be administered over 1 hour.

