### **6.2.2 Day 1 (Randomization)**

On Day 1, study staff will confirm the informed consent and patient's willingness to participate in the study. The patients will be randomized to receive either ANB020 or placebo in a 1:1 ratio (12 patients will receive ANB020 and 12 patients will receive placebo). Additional Day 1 procedures will be carried out in accordance with the Schedule of Events in Table 4.1.

Patients will be allowed to leave the study center 6 to 8 hours after the ANB020/placebo administration and completion of study-specific procedures providing that:

- No AEs have been reported during the study visit.
- The patient responds in the affirmative when asked if they are feeling well.

If any of these conditions are not met, then the patient will only be allowed to leave the study center with the authorization of the Investigator or appropriately qualified delegate.

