#### **7.1.1.1 Reporting of Adverse Events**

All AEs, regardless of severity and whether or not they occurred during the screening (after informed consent), treatment, or follow-up period are to be recorded on the appropriate pages in the eCRF (either ‘serious’ or ‘non-serious’). The Investigator should complete all the details requested including dates of onset, severity, action taken, outcome, and relationship to the IP. Each event should be recorded separately. All AEs that occur within 30 days after the patient’s last visit (EOS visit) should also be reported.

The ANB020 or placebo infusion may be slowed or interrupted for patients experiencing infusion-related AEs. Following the infusion, all patients will be observed for fever, chills, rigors, hypotension, nausea, or other infusion-related AEs.

All SAEs (as described in Section 7.1.1) that occur after the patient has signed informed consent (including the protocol defined follow-up period), regardless of judged relationship to the IP, or after the study period, if considered serious and related to IP or to the patient’s participation in the study, must be reported to IQVIA within 24 hours of the Investigator’s knowledge of the event. The SAE reporting will originate in the electronic data capture (EDC) system and an email will be sent to the designated responsible parties defined in the Safety Plan. The paper SAE form is in place as a back-up in the rare event that EDC is not accessible to the reporter of the SAE and the paper SAE form should be sent to **QLS\[contact]**.

The following documents should be submitted to IQVIA Safety:

- Serious Adverse Event Report Form.
- The following eCRFs or de-identified source documents:
  - Demographics page(s).
  - Medical history page(s).
  - Adverse event page(s).
  - Concomitant medication page(s).
  - Hospital discharge summary: If the patient is hospitalized because of or during an SAE, then a copy of the hospital discharge summary.

The following are the Investigator’s responsibilities:

- Record diagnosis instead of signs and symptoms when available using accepted medical terminology.
- The events recorded on the safety event report form must be consistent with the information entered on the respective CRFs.
- Include any relevant medical history, concurrent illnesses, and concomitant medicines.
- Include treatment(s) provided.
- The Investigator must assess causality at the time of the first SAE notification.

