### 9.1 Determination of Sample Size

The number of patients to be enrolled is not based on statistical power considerations.

A total of approximately 24 patients will be randomized in a 1:1 ratio to receive ANB020 or placebo.

All patients who discontinue the study prior to completing the Day 36 study assessments will be replaced. Patients who are withdrawn from the study after Day 36 will not be replaced.

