3. STUDY DESIGN'

This is a proof of concept study designed to assess the effects of a single 300 mg/100 mL IV dose of ANB020 compared to placebo in adult patients with severe eosinophilic asthma. This study will also assess the safety and tolerability of ANB020 in adult patients with severe eosinophilic asthma.

The screening visit will be conducted 7 to 14 days before Day 1. After obtaining the informed consent from the patients; medical history, concomitant medications, vital signs, physical examination, FeNO measurement, spirometry to determine FEV1, and laboratory tests will be performed at the screening visit.

Eligible patients will be randomized in a 1:1 ratio to receive ANB020 or placebo on Day 1. Specific study assessments and safety laboratory tests will be performed. Blood samples to determine the eosinophil count, ex vivo induced IFN-γ levels, anti-drug antibodies (ADA), serum cytokines, and serial samples for PK analysis will be collected.

All patients will be followed up for 18 weeks. Patients will return to the study center for study

Document: \\ieedc-vnasc01\biosdata\AnaptysBio\ANB020\CYA74392\Biostatistics\Documentation\SAP\Final\20181218 Version Number: 1.0

> Version Date: 18Dec2018

Reference: CS_WI_BS005

Template No: CS_TP_BS016 Revision 4

Effective Date: 01Apr2016

Author:

Clinical Study Report ANB020-004 - Original

AnaptysBio Inc PROTOCOL ANB020-004 Page 12 of 46

IQVIA STATISTICAL ANALYSIS PLAN

> assessments on Day 2, 8, 22, 36, 64, 85, and 106 and will be contacted via telephone by study staff on Day 50 and 57. The EOS visit will be on Day 127 (Week 18) at the study center. All patients will undergo the FeNO and FEV₁ (spirometry) tests at each study center visit. An ACQ-7 will be completed by all patients at each study center visit (except Day 2) and the patient diary must be completed on a daily and weekly basis. The Investigator will rate the patient's response using the CGIC scale and the patients will be asked to rate the degree of change in the overall asthma status using the PGIC scale (part of the diary card). During the follow-up period, assessments including vital signs, safety laboratory testing, eosinophil count, PK, and pharmacodynamic analysis will be performed at specified time points.

Sample Size:

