For TEAE by final outcome, if a patient has multiple TEAEs with different outcomes, worst case will be considered, where 'Fatal' being the worst.

For Action Taken with the Drug, patient can be counted in more than one categories.

The following summary tables will be provided by SOC and PT for each treatment group and overall:

- Number of patients with at least one TEAE o
- Number of patients with at least one serious TEAE 0

Document:

\\ieedc-vnasc01\biosdata\AnaptysBio\ANB020\CYA74392\Biostatistics\Documentation\SAP\Final\20181218

Version Number: 1.0

Reference: CS_WI_BS005

Version Date: 18Dec2018

Template No: CS_TP_BS016 Revision 4

Effective Date: 01Apr2016

Author:

Clinical Study Report ANB020-004 - Original

AnaptysBio Inc PROTOCOL ANB020-004 Page 30 of 46

- Number of patients with at least one TEAE by severity 0
- Number of patients with at least one TEAE by relationship to study drug 0
- Number of patients with at least one TEAE leading to permanent discontinuation of study 0 drug
- Number of patients with at least one TEAE leading to interruption of study drug 0
- Number of patients with at least one TEAE leading to patient withdrawal from study 0
- Number of patients with at least one TEAE leading to death 0
- Number of patients with non-TEAE 0

If an AE occurs more than once, the patient will be counted only once per SOC and once per PT within each SOC. If a patient reports a TEAE more than once within a SOC/PT, the AE with the worst-case severity will be used in the corresponding severity summaries and the worst-case relationship to the study drug will be used in the corresponding relationship summaries.

Percentages will be calculated relative to the total number of patients in the SAF. The summaries will be sorted by descending frequencies of SOC and descending frequencies of PT with in SOC.

Listings will be provided for TEAEs, Serious TEAEs, TEAEs leading to discontinuation from study or from IP, and TEAEs leading to death for the SAF.

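### No planned TEAE table groups infusion-related events or limits them to an acute onset window, so a risk the protocol names is counted per arm only through partial or diluted proxies

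*SAP*

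**What the plan says.** **The risk.** Protocol 2.4 lists possible signs of an allergic reaction and, from experience with other monoclonal antibodies, of cytokine release, including "Mild to moderate fever, chills, headache, nausea, and vomiting". Protocol 5.6 allows the infusion to be slowed or interrupted for infusion-related AEs. Protocol 7.1.1.1 says "Following the infusion, all patients will be observed for fever, chills, rigors, hypotension, nausea, or other infusion-related AEs". Safety and tolerability of the single IV dose is a primary objective (Protocol 3.1).

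**The timing.** The exposure is short: "Infusions will be administered over 1 hour". The observation period is long: "All patients will be followed up for 18 weeks". SAP 18.1 counts as treatment-emergent any AE that starts or worsens from the infusion onward. It sets no end date and no acute sub-period.

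**The tables.** SAP 18.1 states: "The following summary tables will be provided by SOC and PT for each treatment group and overall". The list covers any, serious, by severity, by relationship, and those leading to discontinuation, interruption, withdrawal or death. The shells add a per-arm overview (Table 14.3.1.1, with related TEAEs and action taken) and a PT-only table (14.3.1.2.1). Listing 16.2.7.1 shows every AE with start date, study day, relationship and a field for onset before the investigational product. Neither the SAP text nor the shells contain an infusion-reaction term list, a grouped count or an onset window.

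Protocol 9.4.1 also promises summaries of potentially significant and clinically important AEs. SAP 18.1 neither defines nor tabulates them.

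**The concern.** A reader of the study report will ask how many patients in each arm had a reaction to the infusion. No planned table answers that directly.

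- **Interruption (Table 14.3.1.4).** This is the closest. It omits a reaction that only slowed the infusion, one that started after the hour was over, and one that needed no action.
- **Any TEAE.** This row is close to its ceiling. In Phase I, 81% of "subjects in the placebo group and 79% subjects in the ANB020 group had at least one treatment-emergent adverse event (TEAE) during the study".
- **Related TEAE.** This is less crowded, but Protocol 2.4 gives 44% in both Phase I arms. It covers the whole follow-up and depends on the causality judgement.
- **PT rows.** Patients with chills, pyrexia and nausea may fall in three different rows, mixed with the same symptoms weeks later. Headache is on the cytokine-release list and ran at 31% on placebo and 27% on ANB020 in Phase I.
- **Vital signs (Table 14.3.5.8).** This gives summary statistics by visit, not patients with an event.

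At stake is the clarity of a primary safety objective. An acute excess could sit inside similar-looking whole-period rates, and any later count of it would use terms and a window chosen with the data in view.

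**Working it through.** The plan has no figure to reproduce: "The number of patients to be enrolled is not based on statistical power considerations", and no reaction rate is given. The sums below only compare how visible the same hypothetical excess would be in each row.

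**Inputs**
- Patients per arm: 12, from Protocol 6.2.2 ("12 patients will receive ANB020 and 12 patients will receive placebo").
- Background, any TEAE: 80%, rounded from 81% and 79% in Phase I (Protocol 2.1).
- Background, related TEAE: 44% in both arms (Protocol 2.4).
- Follow-up: 18 × 7 = 126 days.
- Assumed: background events occur at a constant rate over those 126 days, since the Phase I observation period behind the percentages is not stated.
- Assumed: reaction risk r on ANB020 only, 25% with a range of 15% to 33%, independent of background.

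**Background in a two-day window**
- Daily rate = −ln(1 − 0.80)/126 = 0.0128.
- Two-day risk = 1 − exp(−2 × 0.0128) = 2.5%.

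**Excess patients in a row with background b**
- Proportion on ANB020 = 1 − (1 − b)(1 − r).
- Excess = 12 × (1 − b) × r.

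| Row | b | ANB020 v placebo, r = 25% | Excess of 12: r = 15% | r = 25% | r = 33% |
|---|---|---|---|---|---|
| Any TEAE, whole follow-up | 0.80 | 85% v 80% | 0.36 | 0.60 | 0.79 |
| Related TEAE, whole follow-up, all reactions judged related | 0.44 | 58% v 44% | 1.0 | 1.7 | 2.2 |
| Any TEAE with onset Day 1-2 | 0.025 | 27% v 2.5% | 1.75 | 2.9 | 3.9 |

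Moving the any-TEAE background from 79% to 81% gives 0.34 to 0.83 in the first row across the range of r, and 1.75 to 3.86 in the third.

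**Interruption table.** If a fraction f of reactions interrupts the infusion, the expected count at r = 25% is 12 × 0.25 × f = 3f. The documents give no f, so this is anywhere from 0 to 3.

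**Splitting.** Three reacting patients spread evenly over five symptom terms give 3/5 = 0.6 per PT row.

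**Grouping without a window.** Suppose the grouped terms carry a 31% background (the Phase I placebo headache rate) over Days 1 to 127. At r = 25% the whole-period count is 12 × (1 − 0.69 × 0.75) = 5.8 against 12 × 0.31 = 3.7. In Days 1-2 it is about 3.1 against 0.07. Both the grouping and the window are needed.

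**Precision.** Three of 12 has an exact 95% interval of 5.5% to 57.2%. Zero of 12 leaves a two-sided upper limit of 26.5%. Three against zero gives a two-sided Fisher p of 2 × C(12,3)/C(24,3) = 440/2024 = 0.22.

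**The case against.** A reader might infer that TEAEs are shown only by SOC and PT and that infusion reactions are never counted. The documents do not support that. The overview counts each patient once for any, serious, severe and related TEAEs and shows action taken. There are relationship, PT-only and interruption tables. With about 24 patients, a Day 1-2 count can be read by hand from Listing 16.2.7.1, and Listing 16.2.5.1 gives infusion times and the reason for any volume below 100 mL.

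A reader might also take splitting across terms as certain. Protocol 7.1.1.1 asks sites to record a diagnosis in place of symptoms when one is available, so a well-characterised reaction would be one PT. Splitting remains possible when no diagnosis is made, and a patient coded to a diagnosis is still not added to one coded to chills.

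Comparing only with the any-TEAE row would exaggerate the gap. An event during or just after the infusion would plausibly be called possible or probable, and SAP 18.1 maps both to related. That row recovers about 1.7 of the 2.9 patients at r = 25%, if every reaction is so judged.

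Finally, the documents do not suggest that such reactions are frequent. Protocol 2.4 says nothing so far makes an allergic reaction likely, the cytokine-release text comes from other antibodies, and Phase I shows no overall TEAE excess.

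All of this stands. It narrows the point without removing it, because a hand count has no pre-set terms or window, and none of the other tables isolates the acute period.

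**Conclusion.** The gap is real but modest. A risk named in Protocol 2.4, 5.6 and 7.1.1.1, under a primary safety objective, has no pre-specified grouped or time-limited count. The existing tables give partial views: interruption captures a subset, and the any-TEAE and related-TEAE rows dilute an acute excess to roughly one fifth (0.6/2.9) and three fifths (1.7/2.9) of what a Day 1-2 row would show.

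Those ratios rest on the Phase I backgrounds carrying over to these patients, a constant background rate over 126 days, and all reactions being judged related. The reaction risks are illustrations and not estimates. It would be wrong to conclude that ANB020 causes infusion reactions, that the plan would hide them, or that a window would make a difference statistically clear at 12 per arm. SAP 18 plans no statistical comparison of safety data. No planned endpoint or estimate is invalid without the extra table; it is a cheap improvement in reporting.

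**What to change.** Add one descriptive table to SAP 18.1, on the Safety Analysis Set by treatment received:

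1. Number and percentage of patients with at least one TEAE with onset from the start of infusion through Day 2.
2. A sub-row for patients with at least one such event on a pre-listed set of terms, each patient counted once, with the contributing PTs beneath.
3. A second sub-row for patients with any other TEAE in the window judged related. This replaces the open category of other infusion-related AEs, for which the AE listing shell has no flag.

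Build the list from all the signs in Protocol 2.4 and 7.1.1.1: fever, chills, rigors, headache, nausea, vomiting, hypotension, edema, pulmonary infiltrates, rash, wheezing or difficulty breathing, dizziness or fainting, facial or throat swelling, fast pulse and sweating. Add diagnosis-level terms such as infusion-related reaction, hypersensitivity and cytokine release syndrome. Fix it before unblinding, and have it drawn up by staff outside the restricted group that sees unblinded safety listings under SAP 4.2. The same edit could state what became of the potentially significant and clinically important AE summaries in Protocol 9.4.1.

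The cost is one extra table and a term list, with no new data or visits. The listing shell shows start date and study day but no clock time, so the window is in days; Day 1 events can be placed with the field for onset before the product.

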18.2. DEATHS

The number of patients with at least one TEAE leading to death will be summarized as described above.

18.3. LABORATORY EVALUATIONS

The following tests will be conducted throughout the study under laboratory evaluations:

Hematology (Hematocrit, Packed Cell Volume [PCV], Hemoglobin, MCH, MCH concentration, MCV, Platelet count, RBC, WBC [absolute], Basophils [absolute and %], Eosinophils [absolute and %], Monocytes [absolute and %], Neutrophils [absolute and %], Lymphocytes [absolute and %], Immunoglobulins [IgA, IgG, IgM, IgE, IgD])

Clinical Chemistry (ALT, Albumin, ALP, AST, Bicarbonate, Bilirubin [Total], Bilirubin [Direct-if total is elevated], Calcium, Chloride, C-reactive Protein (CRP), Creatinine, GGT, Glucose, Potassium, Phosphate [Inorganic], Protein [Total], Sodium, Troponin, Urea, hCG [WOCBP])

Document: \\ieedc-vnasc01\biosdata\AnaptysBio\ANB020\CYA74392\Biostatistics\Documentation\SAP\Final\20181218 Author:

Version Number: 1.0 Version Date: 18Dec2018

Template No: CS_TP_BS016 Revision 4 Reference: CS_WI_BS005

Effective Date: 01Apr2016

AnaptysBio, ANB020 CONFIDENTIAL IND 126765, SN 0035

Clinical Study Report ANB020-004 - Original

AnaptysBio Inc PROTOCOL ANB020-004 Page 31 of 46

STATISTICAL ANALYSIS PLAN

Urinalysis (Bilirubin, Blood, Glucose, Ketones, Leukocytes, Nitrates, pH, Protein, Specific gravity, and Urobilinogen)

The following tests were conducted only at screening:

Virology (Hepatitis B Surface Antigen, Hepatitis C Antibody, HIV Antibodies)

TB (QuantiFERON TB Gold test)

Drugs of Abuse

FSH

Urine Pregnancy-dipstick (prior to IP administration on Day 1)

The actual and change from baseline values at scheduled assessment for each laboratory parameter will be summarized using appropriate descriptive statistics by treatment groups and all available visits.

Frequency count and percentages will be provided for categorical variables.

The following summaries also will be provided for laboratory data:

Incidence of abnormal values according to normal range criteria

Normal, Abnormal NCS and Abnormal CS by test

Shift table for laboratory test parameters from baseline will be summarized at each visit. Percentages will be based on the number of patients in the SAF population with data at baseline and the visit of interest.

Hematology and clinical chemistry data will be reported in System International (SI) units.

18.4. ECG EVALUATIONS

A standard 12-lead ECG will be performed at screening and EOS visits. The following ECG parameters will be summarized:

Heart Rate (bpm)

PR Interval (msec)

QRS Interval (msec)

QT Interval (msec)

Document: \\ieedc-vnasc01\biosdata\AnaptysBio\ANB020\CYA74392\Biostatistics\Documentation\SAP\Final\20181218

Author:

Version Number: 1.0 Version Date: 18Dec2018

Reference: CS_WI_BS005

Template No: CS_TP_BS016 Revision 4

Effective Date: 01Apr2016

QTc Interval (msec)

QTcF (msec) {based on Fridericia formula}

The actual and change from baseline values for the above parameters will be summarized using descriptive statistics (n, mean, standard deviation, median, and range) by treatment groups and all available visits.

The overall assessment of ECG will be summarized using frequency and percentage of the following indications:

Normal

Abnormal, Not Clinically Significant (ANCS)

Abnormal, Clinically Significant (ACS)

A listing of ECG parameters and of the overall assessment will be provided.

18.4.1.ECG SPECIFIC DERIVATION

Fridericia's Correction (msec)

$$QTcF \text{ (msec)} = \frac{QT \text{ (ms)}}{\sqrt[3]{RR \text{ (ms)}}/1000}$$

18.4.2.ECG MARKEDLY ABNORMAL CRITERIA

Absolute values of the QT interval will be classified as:

≥450 msec

≥480 msec

≥500 msec

Since, there are different ranges for QTcF between the males and females, we will summarise the QTcF by gender as defined below:

Absolute values of the QT interval as: Males: 431- 450 msec; Female: 451- 470 msec.

Abnormal values of the QT interval as: Males: > 450 msec Females: > 470 msec.

Document: \\ieedc-vnasc01\biosdata\AnaptysBio\ANB020\CYA74392\Biostatistics\Documentation\SAP\Final\20181218 Version Number:

Author:

Version Date: 18Dec2018

Reference: CS_WI_BS005

Template No: CS_TP_BS016 Revision 4

Effective Date: 01Apr2016

Clinical Study Report ANB020-004 - Original

AnaptysBio Inc PROTOCOL ANB020-004 Page 33 of 46

STATISTICAL ANALYSIS PLAN

The change from Baseline of QT interval will be classified as:

>30 msec increase from baseline

>60 msec increase from baseline

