#### **9.4.2 Vital Signs Measurements, Physical Findings, and Clinical Laboratory Evaluations**

Summaries and listings of vital signs, physical examination, ECG, and laboratory test results will be presented. Appropriate descriptive statistics will be summarized for the observed value at each scheduled assessment and for the corresponding change from Baseline.

For hematology and clinical chemistry, listings will also flag up any abnormal or out-of-range values. Clinically significant changes in the laboratory test parameters will be summarized and listed. Hematology and clinical laboratory data will be reported in System International units.

For ECG variables, the QT correction factor will be based on both the Bazett and Fridericia formulae (QTcB and QTcF). Categorical summaries of absolute QT, QTcB, and QTcF values and change from (Baseline) values in QT, QTcB, and QTcF values will be presented by treatment and visit.

Descriptive statistics will be used to present the safety outcomes including, physical examination results, weight, BMI, vital signs, laboratory test results, and ECG results. Change from Baseline will also be summarized for vital signs measurements and clinical laboratory test results.

Number of asthma exacerbations will be summarized using frequency count and percentage. Time (in days) from randomization to the first asthma exacerbation will be used as a supportive variable and will be calculated as follows:

Start date of first asthma exacerbation – Date of randomization + 1.

The time to first asthma exacerbation for subjects who do not experience an asthma exacerbation during the period till end of study will be censored at the date of their last visit, or at the time point after which an exacerbation could not be assessed (for lost to follow-up patients).

Time to first asthma exacerbation will be analyzed to explore the extent to which treatment delays the time to first exacerbation compared with placebo. A cox proportional hazard model will be deployed by using treatment group as a class variable and number of exacerbations in the study as covariates. Results of the analysis will be summarized as hazard ratios and 95% confidence intervals (CIs) comparing ANB020 with placebo.

Time to first asthma exacerbation will be displayed graphically using a Kaplan-Meier plot. The median time to event will be summarized by treatment, if there is sufficient uncensored data available to calculate these median values.

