- Baseline will be last non-missing measurement taken prior to reference start date (including unscheduled assessments or retests)

Programming Note (not part of table): Continue the table for all parameters and all available visits

Document: \\ieedc-vnasc01\biosdata\\AnaptysBio\ANB020\CYA74392\Biostatistics\Documentation\SAP\Final\20181218

Author: Version Number: 1.0

Version Date: 18Dec2018

Table Shells

AnaptysBio Inc. PROTOCOL ANB020-004 Page 47 of 51

 ${\bf Table~14~3~5~7}$ Summary of QT Changes from Baseline to Last Observation – Safety Analysis Set

	ANB020	Placebo	Total	
	(N=XX)	(N=XX)	(N=XX)	
Mean change [a] in QT Interval (msec) from baseline	xx (xx x)	xx (xx x)	xx (xx x)	
	xx (xx x)	xx (xx x)	xx (xx x)	
Number (%) of patients reaching a value in QT Interval				
Males:				
Females:				
Total				
>450 (msec)	xx (xx x)	xx (xx x)	xx (xx x)	
>480 (msec)	xx (xx x)	xx (xx x)	xx (xx x)	
>500 (msec)	xx (xx x)	xx (xx x)	xx (xx x)	
Number (%) of patients experiencing an increase in QT Interval	xx (xx x)	xx (xx x)	xx (xx x)	
>30 (msec)	xx (xx x)	xx (xx x)	xx (xx x)	
>60 (msec)	xx (xx x)	xx (xx x)	xx (xx x)	
Number (%) of patients experiencing a decrease in QT Interval	,	,	,	
>30 (msec)				
>60 (msec)				
Mean change [a] in QTcF Interval (msec) from baseline				
Number (%) of patients reaching a value in QTcF Interval				
>450 (msec)				
>480 (msec)				
>500 (msec)				

Source: Listing 16 2 8 2

Note

QTcF = Fridericia's correction for QT;

N is the number of patients under Safety Analysis Set

Baseline will be last non-missing measurement taken prior to reference start date (including unscheduled assessments or retests)

[a] Change from baseline to last observation

Programming note: Please refer SAP for the male and female reference ranges

Document: \\ieedc-vnasc01\biosdata\\AnaptysBio\ANB020\CYA74392\Biostatistics\Documentation\SAP\Final\20181218

Author: Version Number: 1.0

Version Date: 18Dec2018

CONFIDENTIAL

[figure not shown]

Table Shells

AnaptysBio Inc. PROTOCOL ANB020-004 Page 48 of 51

Table 14 3 5 8 Vital Signs – Safety Analysis Set

				ANB020 (N=XX)		Placebo (N=XX)	Total (N=XX)	
Parameter (Unit)	Visit	Statistics	Actual	Change from Baseline	Actual	Change from Baseline	Actual	Change from Baseline
Pulse Rate (bpm)	<visits></visits>	n Mean (SD) Median Min, Max	xx xx x (xx xx) xx x xx, xx		xx xx x (xx xx) xx x xx, xx		xx xx x (xx xx) xx x xx, xx	- - -
espiratory Rate (resp/min)	<visits></visits>							

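### The SAP's categorical ECG change analysis covers uncorrected QT only, although the protocol also calls for QTcB and QTcF, and the sex-specific QTcF ranges are labelled as QT

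*SAP*

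**What the plan says.** Protocol 9.4.2 bases the QT correction on both the Bazett and the Fridericia formulae, and then states: "Categorical summaries of absolute QT, QTcB, and QTcF values and change from (Baseline) values in QT, QTcB, and QTcF values will be presented". These are to be given for each arm at each visit. The protocol sets no numerical cut-offs.

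SAP 18.4.2 supplies cut-offs. For change it says "The change from Baseline of QT interval will be classified as" increases above 30 and above 60 msec. It then announces a summary of QTcF by gender, but words the ranges as "Absolute values of the QT interval as: Males: 431- 450 msec; Female: 451- 470 msec", with the abnormal limits (above 450 msec for males, above 470 msec for females) also worded as QT.

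Shell Table 14.3.5.7 follows the same pattern. The row "Number (%) of patients experiencing an increase in QT Interval" carries the 30 and 60 msec categories, and the male and female rows sit in the QT block. QTcF has a mean change and absolute categories above 450, 480 and 500 msec, but no change categories. SAP 18.4 lists QTcF and a QTc interval whose correction is not stated. QTcB is not named anywhere in the SAP. SAP 3.2 declares only the intermediate analyses as a change from the protocol.

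On timing, SAP 18.4 says "A standard 12-lead ECG will be performed at screening and EOS visits". The schedule of events in Protocol Table 4.1 agrees, with the EOS procedures also done at an early termination visit.

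**The concern.** ECG is one of the safety endpoints listed under the primary endpoints in the protocol synopsis. Categorical change is the part of the ECG analysis that picks out individual patients with a large shift from their own baseline. Uncorrected QT shortens as heart rate rises and lengthens as it falls. A category defined on it therefore mixes repolarisation change with heart-rate change. It can stay empty when corrected QT has risen, and can fill when corrected QT has not moved. The protocol's list of QT, QTcB and QTcF would have avoided this.

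The wording of the sex-specific ranges adds a programming risk. The lead-in sentence points to QTcF, while the ranges and the shell point to QT. Whoever follows the shell will apply the ranges to the wrong variable.

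**Working it through.** **1. The plan's variables side by side**

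| Variable | Protocol 9.4.2, absolute categories | Protocol 9.4.2, change categories | SAP 18.4.2 and shell 14.3.5.7, absolute | SAP 18.4.2 and shell 14.3.5.7, change |
|---|---|---|---|---|
| QT | yes | yes | yes | yes (>30, >60 msec) |
| QTcF | yes | yes | yes (>450, >480, >500 msec) | no |
| QTcB | yes | yes | not named | not named |

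**2. How heart rate enters**

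Fridericia: QTcF = QT / (RR/1000)^(1/3), with RR = 60,000/HR in msec. Hence QT = QTcF × (60/HR)^(1/3).

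The factors are 1 at 60 bpm, (60/80)^(1/3) = 0.9086 at 80 bpm, and (60/90)^(1/3) = 0.8736 at 90 bpm. The QTcF values and heart rates below are illustrative assumptions, not study data.

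*A rise that is missed (female patient).*
- Baseline: QTcF 385 at 60 bpm gives QT = 385 × 1 = 385 msec.
- Follow-up: QTcF 447 at 90 bpm gives QT = 447 × 0.8736 = 390.5 msec.
- QTcF change: 447 − 385 = +62 msec. QT change: 390.5 − 385 = +5.5 msec.
- Check against every planned category: QT change is below 30; absolute QT is below 450; absolute QTcF of 447 is below 450; and 447 is below the female range of 451–470, even if that range is applied to QTcF. No category is triggered.

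*A flag with no QTcF change.*
- Baseline: QTcF 420 at 80 bpm gives QT = 420 × 0.9086 = 381.6 msec.
- Follow-up: QTcF 420 at 60 bpm gives QT = 420 msec.
- QT change: +38.4 msec, counted as above 30 msec. QTcF change: 0.

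At QTcF 420 msec, a fall from 75 to 60 bpm is already enough: 420 × [1 − (60/75)^(1/3)] = 30.1 msec.

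**3. Drug remaining at the post-dose ECG**

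The documents give no residual figure for Day 127. Their nearest figure is in Protocol 4.3.4, where five half-lives are put at about 70 days. This reproduces with a half-life of 14 days (5 × 14 = 70), the lower end of the range in Protocol 2.1: 14–17 days after single doses, and 16–20 days after multiple IV doses.

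Day 127 is 126 days after the dose. Assuming mono-exponential decline, the fraction left is 2^(−126/t½):

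| Half-life (days) | Half-lives elapsed | Drug left at Day 127 |
|---|---|---|
| 14 | 9.0 | 0.20% |
| 16 | 7.9 | 0.43% |
| 17 | 7.4 | 0.59% |
| 20 | 6.3 | 1.27% |

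The ±2-day visit window widens the range to 0.18–1.36%. For half-lives of 14–20 days, the same formula gives 95–97% on Day 2, 71–78% on Day 8 and 35–48% on Day 22. None of those visits has a scheduled ECG.

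**The case against.** Several points on the other side stand.

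- **Corrected QT is not ignored.** Shell Table 14.3.5.6 summarises QTcF change as a continuous variable, Table 14.3.5.7 has absolute QTcF cut-offs, and Listing 16.2.8.2 shows each patient's change from baseline. A reader might infer that any large QTc rise would go unseen. That is too strong: a rise in QTcF from 420 to 480 msec would be counted in the QTcF row above 450 msec, whatever the heart rate. Only rises that end below the absolute limits escape the categories, and with about 24 patients they could still be found in the listing.
- **The SAP was written to a later protocol.** It cites Amendment 4 of 31 October 2018; the protocol supplied ends at Amendment 3. Section 9.4.2 may have changed, so an undeclared departure is shown only against Amendment 3.
- **QTcB may not have been dropped.** The unspecified QTc interval could be Bazett-corrected. The documents do not say.
- **Salbutamol is not an established cause of heart-rate shifts here.** Protocol 6.1.2 asks for post-bronchodilator spirometry with 400 µg salbutamol at all clinic visits, but the note to SAP Listing 16.2.6.2 says post-bronchodilator readings were captured on Day 1 only, when no ECG is scheduled. The passages need to be reconciled; the heart-rate argument does not depend on them.
- **There is no ECG signal to chase.** The protocol does report "One subject in the ANB020 40 mg dose group, had an increased troponin level", but the same account of Phase I says that the level returned to normal and that no significant ECG changes were noted, at IV doses up to 750 mg.

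It can also be said that refining categories matters little if the ECG is taken when almost no drug is left. That lowers the stakes, but it does not justify a category on the wrong variable.

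**Conclusion.** The point holds as a limited gap in the ECG safety analysis. Against Amendment 3, the SAP omits the categorical change summaries for QTcF and QTcB, labels QTcF ranges as QT, and does not declare this. The consequence is that the change categories can miss a QTcF increase of 62 msec and can flag a QT increase of 38 msec with no QTcF change, under plausible but assumed heart rates. The continuous QTcF summary and the absolute QTcF cut-offs are unaffected.

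The timing is a secondary limit on interpretation. With half-lives of 14–20 days and mono-exponential decline, about 0.2–1.3% of drug is left at the Day 127 ECG. A reader might infer that the study can say nothing at all about ECG effects. The documents do not support that: a lasting effect could still appear on Day 127, and a patient who leaves early has an ECG at that visit. What the scheduled tables cannot support is a conclusion, in either direction, about effects while drug is present.

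**What to change.** - In SAP 18.4.2 and shell Table 14.3.5.7, apply the 30 and 60 msec change categories to QTcF. Word the sex-specific ranges as QTcF, and move the male and female rows to the QTcF block.
- Add the same categories for QTcB, or declare its removal in SAP 3.2, after checking section 9.4.2 of Amendment 4. State which correction the QTc interval in SAP 18.4 uses.
- Keep uncorrected QT as a descriptive summary.
- Add one sentence to SAP 18.4 and to the report: the ECG tables describe screening against Day 127 or early termination, and do not support a conclusion about effects while drug is present.

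The cost is small. QTcF is already derived, so the first item is a few table rows and some wording. QTcB needs one more derivation from the same QT and heart-rate data. No additional recording is needed. If the database has already been locked, SAP section 1 requires the change to go into a SAP amendment.
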